730 18-22 month clinic visit because of acute illness, behavior problems, or "other" reasons,  
731 appointments will be re-scheduled until the evaluation is complete.  
732

733 **4.14 Primary Outcome:** The primary outcome will be death or disability (either  
734 moderate or severe in extent) at 18-22 months of age. *Severe disability* will be defined  
735 by any of the following: a Bayley III Cognitive score < 70, Gross Motor Functional  
736 (GMF) Level of III-V, blindness or profound hearing loss (inability to understand  
737 commands despite amplification). *Moderate disability* will be defined as a Bayley  
738 Cognitive score 70-84 and either a GMF level of II, a currently active seizure disorder, or  
739 a hearing deficit requiring amplification to understand commands. Infants without the  
740 primary outcome will be categorized as normal or mildly impaired. *Normal* will be  
741 defined by a cognitive score  $\geq 85$  and absence of any neurosensory deficits. *Mild*  
742 *impairment* will be defined by a cognitive score 70-84, or a cognitive score  $\geq 85$  and any  
743 of the following: presence of a GMF level 1-II, seizure disorder or hearing loss not  
744 requiring amplification.  
745

746 **4.15 Secondary Outcomes:** These include number of deaths in the NICU and following  
747 discharge, number of infants with mild, moderate and severe disability, number of infants  
748 for whom aggressive care is withdrawn, adverse events (severe bradycardia, acidosis,  
749 bleeding, thrombotic or ischemic CNS abnormalities), clinical neonatal seizures and  
750 severe neonatal MRI abnormalities (defined by the NRN study evaluating MRI  
751 abnormalities). The treatment effect on the primary outcome by level of encephalopathy  
752 (with the understanding that the study is not powered for this analysis) will be evaluated.  
753 The MRI will be obtained between 7-14 days of age because of ongoing changes in brain  
754 injury; this timing is later than recommended by the Quality Standards Subcommittee of  
755 the American Academy of Neurology and the Practice Committee of the Child Neurology  
756 Society (Ment 02). If it is found that clinical MRI studies are performed outside this  
757 window as part of usual care at participating centers, the studies performed closest to day  
758 7 may need to be evaluated separately from those performed after 8 days of age since  
759 cooling may delay the evolution of brain lesions and imaging performed too soon after  
760 hypothermia may not reflect the ultimate appearance of lesions. Once the MRI secondary  
761 study is approved, two central readers (Drs [name] and [name]) will  
762 evaluate the clinical MRI on a rolling basis, within 1 month of MRI being shipped to the  
763 central readers. The intra-observer reliability of the central readers will be established  
764 prior to initiation of the readings.

765

766 **Primary outcome**---death or disability (moderate or severe) at 18-22 months of age

767 **Secondary outcomes**

768 Normal infants

769 Mildly disabled infants

770 Mortality (including support withdrawn)

771 Cognitive outcome

772 Cerebral palsy

773 Disability by stage of HIE

774 Visual impairment

775 Hearing impairment

776 Multiple disabilities

777 Acute adverse events

778 Multiorgan dysfunction

779 Neonatal seizures

780 MRI findings (based on NICHD summary classification)

781 Length of hospital stay

782 Rehospitalizations after discharge

783 Post neonatal deaths

784 Growth parameters at follow up

785 Bayley III Motor score

786

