2. A second analysis was performed to understand why some infants in the hypothermia group had excessive decreases in temperature (either following the initial overshoot or after achieving equilibration) because this information may enable us to target specific approaches among those infants who we have predicted would tolerate deeper temperatures less well. We compared the perinatal characteristics (age of randomization, 10 minute Apgar score, cord pH, and base deficit) and neonatal characteristics (birth weight, seizures at randomization, level of encephalopathy and inotropic support at randomization) between infants who had no temperatures recorded below 32°C after the initial overshoot compared to those infants who had a temperature of less than 32°C after the initial overshoot and those who had a temperature of < 32°C after achieving equilibration. As noted in Table 3, there were no significant differences between the infants who did not have an overshoot below 32°C and those who dropped their temperatures < 32°C after the overshoot or after equilibration. *There is however a trend for a greater need for inotropic support at randomization between those infants who dropped their temperature below 32°C after initial overshoot (7/17 or 41%) and those who dropped their temperatures after equilibration (6/10 or 60%) compared to those who had no drops below 32°C (20/74 or 27%).*

**Table 3:** Hypothermia infants—comparison of infants with esophageal temperatures < 32°C after initial overshoot or equilibration.

	No drops below 32°C after initial overshoot (N=74)		Esop. temp. < 32°C after initial overshoot (N=17)		Esop. temp. < 32°C after equilibration (N=10)		p-value (Fisher's Exact Test)
	N	%	N	%	N	%	
Outborn	34	46%	9	53%	4	40%	0.85
Male gender	36	49%	12	71%	3	30%	0.11
10 minute apgar ≤ 5 *	59	86%	11	73%	9	90%	0.52
Seizures at randomization	30	41%	10	59%	4	40%	0.38
Severe level of initial HIE †	22	30%	6	35%	3	30%	0.94
Moderate level of initial HIE	51	70%	11	65%	7	70%	
Inotropic support at randomization	20	27%	7	41%	6	60%	0.08

\* 7 infants are missing this data, N=94. Five are in the first group (N=69), and two are in the middle group (N=15). † 1 infant is missing initial HIE in the first group (N=73).

490  
 491  
 492  
 493  
 494  
 495  
 496  
 497  
 498  
 499

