574 no adverse events ([name] 02) before the whole body hypothermia trial was initiated  
575 with cooling to 33.5°C.  
576

577 **4.3 Inclusion Criteria:** The inclusion criteria are similar to the first whole body  
578 hypothermia for HIE trial ([name] 05). All infants with a gestational age  $\geq 36$  weeks  
579 will be screened for study entry if they are admitted to the NICU with an admitting  
580 diagnosis of fetal acidosis, perinatal asphyxia, neonatal depression or encephalopathy.  
581 Infants will be evaluated by physiological criteria, followed by a neurological  
582 examination. Eligibility criteria will include a pH  $\leq 7.0$  or a base deficit  $\geq 16$  mEq/L  
583 on umbilical cord or any postnatal sample within 1 hour of age. If, during this interval, a  
584 pH is between 7.01 and 7.15, a base deficit is between 10 and 15.9 mEq/L, or a blood gas  
585 is not available, additional criteria will be required. These include an acute perinatal  
586 event and either a 10-minute Apgar score  $\leq 5$  or assisted ventilation initiated at birth and  
587 continued for at least 10 minutes. Once these criteria are met, all infants will have a  
588 standardized neurological examination performed by a certified physician examiner.  
589 Infants will be candidates for the study when encephalopathy or seizures are present.  
590 Encephalopathy will be defined as the presence of 1 or more signs in 3 of the following 6  
591 categories: 1) level of consciousness: lethargy, stupor or coma; 2) spontaneous activity:

decreased, absent; 3) posture: distal flexion, decerebrate; 4) tone: hypotonia, flaccid or hypertonia, rigid; 5) primitive reflexes: a) suck, weak, absent; b) Moro, incomplete, flaccid; and 6) autonomic nervous system: a) pupils: constricted, unequal, skew deviation or non reactive to light; b) heart rate: bradycardia, variable heart rate or c) respiration: periodic breathing, apnea. Infants will be classified as moderate or severe encephalopathy based on a predefined algorithm. Determination of the stage of encephalopathy will be based on a modified Sarnat stage by scoring the presence of moderate or severe abnormalities in 6 categories. The number of moderate or severe signs determines the extent of encephalopathy and if signs are equally distributed the designation of moderate or severe encephalopathy will be based on the level of consciousness. Multiple births will be enrolled in the same arm of the study.

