667 **4.10 Post Randomization Exclusion of Infants:** The study is designed as intent-to-  
668 treat, and therefore infants will not be excluded after randomization.

669  
670 **4.11 Safety Monitoring of Control and Experimental Infants:**

- 671 a. Skin, esophageal, axillary, and servo set point temperature will be monitored  
672 every 15 minutes for the first 4 hours, every hour up to 12 hours, followed by  
673 every 4 hours during the maintenance phase of cooling and every 2 hours during  
674 the rewarming phase until normothermia is achieved.
- 675 b. Metabolic status: serum electrolytes will be monitored as per clinical routine.

- 676 c. Respiratory status: blood gases will be monitored every 4 to 6 hours. Since  
677 lower target temperatures (< 33.5°C) may be associated with risk of pulmonary  
678 hypertension, more frequent gas measurements may be required.
- 679 d. Cardiovascular: heart rate, blood pressure and use of inotropic agents will be  
680 recorded at baseline and every 4 hours throughout the study period. The risk of  
681 cardiac arrhythmia may be increased at < 33.5°C hence risk will be monitored  
682 along with treatment for arrhythmia. Echocardiograms will be performed as per  
683 site practice.
- 684 e. Renal status: urine output and body weight will be recorded daily during the  
685 intervention interval. Serum BUN and creatinine will be obtained at baseline  
686 and daily as per clinical routine.
- 687 f. Neurological status: To monitor for possible sagittal sinus thrombosis, a subset  
688 of infants will require a cranial sonogram performed within 48-72 hours  
689 following the end of the intervention period. Neurological examinations will be  
690 performed at baseline, following study intervention, pre-discharge and at time  
691 of withdrawal of support. The presence of seizures at baseline, during  
692 intervention and during rewarming will be recorded. All infants with clinical  
693 seizures will have EEG evaluations performed.
- 694 g. Hematological: Platelet counts will be obtained daily. PT/PTT will be obtained  
695 per clinical routine or if bleeding is suspected based upon clinical symptoms or  
696 an unexplained fall in hematocrit by more than 10%. Complete blood counts  
697 will be monitored as per clinical routine, including white blood counts and  
698 absolute neutrophil counts because of potential risk of infection. Since increased  

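### The seizure outcome in Section 4.15 is not limited to events after randomization, and its model leaves out baseline seizures, an entry finding present in about 44% of cooled infants in the earlier trial

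*Protocol*

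**What the plan says.** The secondary outcomes in Section 4.15 include the number of infants "for whom aggressive care is withdrawn, adverse events (severe bradycardia, acidosis", and the sentence goes on to "bleeding, thrombotic or ischemic CNS abnormalities), clinical neonatal seizures and" severe MRI findings. The list that closes the section repeats "Neonatal seizures" as an item of its own. Neither place gives a time from which events count.

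Section 4.3 describes who can enter. Once the physiological criteria are met, "Infants will be candidates for the study when encephalopathy or seizures are present". A low pH or a large base deficit, in cord blood or in a sample from the first hour, is one physiological route to entry. Among the autonomic signs is "heart rate: bradycardia, variable heart rate".

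Section 4.11, item f, separates the periods in its data collection: "of withdrawal of support. The presence of seizures at baseline, during" the intervention and during rewarming is to be recorded. Section 5.2 specifies robust Poisson models for binary primary and secondary outcomes, adjusted for the two stratification variables, level of encephalopathy and site. Section 3.1 lists "seizures at randomization" among the characteristics compared in the earlier trial, and Table 3 gives the counts.

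**The concern.** A seizure at three hours of age in an infant randomized at five hours is a clinical neonatal seizure in the ordinary sense, yet no allocated treatment can have affected it. If such events count, both sides of each margin carry the same block of fixed events. Randomization balances that block on average, so the problem is not confounding. It pulls the risk ratio toward 1 and shrinks the risk difference. Baseline seizure status is also likely to predict later seizures, and the stated model does not use it although it will be recorded.

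For acidosis and severe bradycardia, which Section 4.15 lists as adverse events, the same dilution would work in favour of the hypotheses of no increase in acute adverse events (Section 4.2, items 2a and 2b). There the risk is that harm is masked.

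**Working it through.** **Baseline share from the Protocol.** The row for seizures in Table 3 gives 30/74 (41%), 10/17 (59%) and 4/10 (40%). Pooled: (30 + 10 + 4)/(74 + 17 + 10) = 44/101 = 43.6%, Wilson 95% interval 34% to 53%. These are cooled infants of the earlier trial only. Section 4.3 calls the present inclusion criteria similar to that trial's.

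**Effect of counting baseline seizures.** Let b be the share with seizures at baseline and p the risk of a first seizure after randomization in the others.

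- Risk of any neonatal seizure: b + (1 − b)p.
- Risk difference: (1 − b)(p0 − p1). With b = 0.436 the multiplier is 0.564, whatever the values of p0 and p1.
- Risk ratio: [b + (1 − b)p1]/[b + (1 − b)p0].

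**Illustration.** The Protocol gives no rate for later seizures and no effect on them. Assumed: p0 from 20% to 40% and a true risk ratio of 0.70. Power is by normal approximation, two-sided 5%, with 363 infants per margin for any seizure and 363 × 0.564 ≈ 205 for new onset.

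| p0 vs p1 | Any seizure, baseline counted | Apparent risk ratio | Risk difference, true → apparent (points) | Power, any seizure | Power, new onset only |
|---|---|---|---|---|---|
| 20% vs 14% | 54.9% vs 51.5% | 0.94 | 6.0 → 3.4 | 15% | 37% |
| 30% vs 21% | 60.5% vs 55.4% | 0.92 | 9.0 → 5.1 | 28% | 55% |
| 40% vs 28% | 66.2% vs 59.4% | 0.90 | 12.0 → 6.8 | 47% | 73% |

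For b between 30% and 55%, the apparent risk ratio runs from 0.86 to 0.96 over the same values of p0.

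**Counting seizures after randomization in all infants.** Let a share q of infants with baseline seizures seize again, with the same risk ratio of 0.70 applying to them. The control risk is bq + (1 − b)p0 and the comparison risk is 0.70 times that, so the ratio stays at 0.70. With q assumed to be 50% to 70%:

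- lowest case (q = 0.5, p0 = 0.20): 0.218 + 0.113 = 33.1% vs 23.2%, power 85%;
- highest case (q = 0.7, p0 = 0.40): 0.305 + 0.226 = 53.1% vs 37.2%, power 99%.

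This count avoids the dilution and keeps every randomized infant. New onset alone also keeps the ratio at 0.70 but drops about 44% of infants. The gain from the covariate was not calculated.

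**The case against.** A reader might infer that the listed outcomes do dilute the treatment effect. The Protocol does not support that: nowhere does it say that baseline events count. Section 4.11f collects seizures by period, so a count after randomization is available from the planned data. Section 2.6 shows that the earlier trial's seizures were compared at baseline, 24, 48 and 72 hours. The counting rule may also sit in an analysis plan or manual that is not shown. All of this stands, which is why the dilution is stated as conditional. What remains is that Section 4.15 does not say which recorded period is the outcome, and that the model Section 5.2 does state omits baseline seizure status.

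A reader might also put acidosis and bradycardia on the same footing as seizures. The overlap there is weaker. Entry acidosis is a cord or first-hour value and only one route to entry. Entry bradycardia is one optional sign, whereas the outcome is severe bradycardia. Both outcomes are adverse events, which are naturally read as occurring on treatment, and the Protocol gives no baseline rate for either.

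Finally, a reader might want ischemic CNS abnormalities reported only as an efficacy outcome, because ischemic injury is the disease under treatment. Section 5.3 makes central MRI reading for infarct or hemorrhage part of safety monitoring, so they should stay among the safety events. The events that Section 5.3 names for sequential monitoring are arrhythmia requiring therapy and major bleeding or thrombosis; seizures and acidosis are not among them.

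**Conclusion.** The point holds in a limited form and is minor. The seizure outcome has no start time although seizures are an entry finding, and the stated model leaves out a baseline variable that will be recorded. If baseline seizures were counted, the risk difference would fall to about 56% of its size. That factor rests on 44/101 from the earlier trial's cooled arm applying here. The apparent risk ratios of 0.94 to 0.90 and all the power figures rest further on assumed later-seizure rates, recurrence rates and a true ratio of 0.70, and serve only as illustration.

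The figures also assume that the allocated treatment acts on every seizure after randomization. For the duration margin, both groups are assigned the same cooling up to 72 hours, so a count from randomization still includes a period in which their assigned treatment does not differ.

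No size can be given for acidosis or severe bradycardia. The primary outcome and the sample size of 363 per margin (726 in total) are unaffected.

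**What to change.** 1. In Section 4.15 and its closing list, define the seizure outcome as clinical seizures after randomization, during the intervention and rewarming periods that Section 4.11f already records, in all randomized infants.
2. In Section 5.2, add baseline seizures as a covariate to the robust Poisson model for this outcome.
3. Report new-onset seizures among infants without baseline seizures as a supportive analysis. It is a subset defined at baseline, so comparisons within it remain randomized, but it has fewer infants.
4. State that acidosis and severe bradycardia, as adverse events, are counted from the start of the intervention. Reconcile the unqualified acidosis in Section 4.15 with Section 4.8, where the acidosis named is the persistent kind.

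The cost is a few sentences and one covariate. Baseline seizures and baseline heart rate are already to be recorded, and blood gases are monitored every 4 to 6 hours, so no new data are needed.

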## 787 **5. STATISTICAL CONSIDERATIONS**

788

789 **5.1 Sample Size:** Sample size calculations for this 2x 2 factorial design assume that there  
790 are no large statistical interactions between the 2 factors being tested --- longer and  
791 deeper cooling. Note that this does not preclude us from testing for the presence of such  
792 an interaction (indeed, it figures as the first secondary hypotheses presented earlier), but  
793 that we are not powering the trial to detect such an interaction.

794

795 In a 2 by 2 factorial design we are essentially superimposing one trial on another -- in this  
796 case, a trial of longer vs. usual duration of cooling, and a trial of deeper vs. usual depth of  
797 cooling. So, unless we want to power for a statistical interaction (which we are not doing  
798 here), we power such a trial for a comparison between the 2 groups ("outside the table",  
799 or marginal analysis) -- longer vs. usual duration of cooling (regardless of depth of  
800 cooling), i.e., groups X vs. Y in Fig. 2 or deeper vs. usual depth of cooling (regardless of  
801 duration of cooling), i.e., groups A vs. B in Fig. 2.

802

803 The following event rates in the 4 cells of the factorial trial design are assumed:  
804 AX=45%, AY=BX=30%, BY=25%. An event rate of 45% for the control group (standard  
805 duration of cooling for 72 hours and standard depth of cooling to 33.5°C) is assumed  
806 based on the primary outcome of the NICHD RCT of whole body hypothermia for HIE  
807 ([name] 05). An event rate of 30% in AY and BX is an estimate. We acknowledge the  
808 event rates will depend on proportion of infants with moderate and severe HIE. We  
809 assume that BY (with the longer and deeper cooling combined) would have the lowest  
810 event rate of 25%. However, we are aware that this group may also be at highest risk for

811 complications of longer and deeper cooling. Assuming that we are principally interested  
812 only in testing the marginal effects of A vs. B or X vs. Y (which translates into a  
813 comparison of event rates of 37.5% vs. 27.5%), a sample size of 363 per group (A or B,  
814 or X or Y), for a total of 726, is needed with a two-tailed test, with Type I error set at 5%,  
815 power set at 80%, and allowing for 5% loss to follow up.

816

817 Two approaches will be used to monitor duration of the trial. Sites will be encouraged to  
818 increase the number of certified examiners, so that no eligible infant is missed. Secondly,  
819 the total duration of enrollment will be limited to 5 years.

820

821 It is possible that randomization would be discontinued for one group because of an  
822 unacceptable rate of adverse events in the neonatal period. In this scenario, more infants  
823 would then be randomized to the other three groups during the remainder of the trial.  
824 Assuming that the overall enrollment rate was unaffected, the number of patients would  
825 be increased for each of the three remaining groups over the number had infants been  
826 randomized to four groups. The power to conduct analyses at the margins as  
827 conventionally performed for a factorial trial would be decreased. However, there would  
828 no longer be interest in whether to use a treatment which has an unacceptable neonatal  
829 adverse event rate. With greater enrollment in the 3 remaining groups, the power to  
830 compare these specific 3 groups would not be compromised and in actuality would be  
831 somewhat higher than had the study been conducted as originally planned. (The same  
832 thinking would apply in the unlikely event that randomization was discontinued in two  
833 groups.)

834

835 **5.2 Data Analyses.** All data analyses will be performed according to the intention-to-  
836 treat principle. There are 2 main outcomes of this factorial design –effect of 120 hours  
837 cooling vs. 72 hours cooling and effect of 32.0°C vs. effect of 33.5°C, hence “at the  
838 margins” analyses will be carried out, testing for differences between groups X and Y,  
839 and groups A and B, from Fig. 2 (McAlister 03). We are aware that such “at the  
840 margins” analysis underestimates the efficacy of the new therapies when the interaction is  
841 antagonistic, while it overestimates efficacy when the interaction is synergistic  
842 (McAlister 03). On the other hand, “inside the table” analyses (pair-wise comparisons of  
843 groups BX, AY and BY, with group AX) use only half as many patients; the confidence  
844 intervals around treatment estimates are much wider for “inside the table” than for “at the  
845 margin” analysis and the use of the same control group (33.5 °C for 72 hours) creates a  
846 problem with multiple comparisons. Since our trial is not expressly powered for this  
847 purpose, “inside the table” analyses will only be pursued in this protocol as a secondary  
848 objective to test for statistical interactions.

849

850 The data in the two groups in the factorial design will be analyzed for treatment group  
851 differences with Chi square or Fisher’s exact tests for the categorical variables and with t-  
852 tests for the continuous variables. The primary and secondary outcomes will be analyzed  
853 using robust Poisson regression models (for binary outcomes) to generate risk ratios  
854 adjusting for the stratification variables (level of HIE and site). The NICHD NRN DSMC  
855 will monitor progress of the study for safety at pre-specified time points. The DSMC will

856  
857  
858  
859  
860  
861  
862  
863  
864

be required to evaluate safety of greater depth and longer duration of cooling after the every 25 infants have been enrolled in the trial.

The Bayesian analyses for different scenarios are note below:

Factorial design with total of 726 subjects (363 per group, A or B, or X or Y) comparing event rates of 37.5% vs. 27.5%

	Posterior Probability of Benefit					
	>0% reduction in death or impairment		>10% reduction in death or impairment		>20% reduction in death or impairment	
	Prior	Posterior	Prior	Posterior	Prior	Posterior
Perspective						
Neutral	.50	.997	.37	.96	.25	.72
Skeptical	.30	.99	.21	.94	.13	.67

865  
866  
867  
868  
869

Factorial design with a total of 726 subjects (363 per group) comparing event rates of 35% vs. 30%

	Posterior Probability of Benefit					
	>0% reduction in death or impairment		>10% reduction in death or impairment		>20% reduction in death or impairment	
	Prior	Posterior	Prior	Posterior	Prior	Posterior
Perspective						
Neutral	.50	.92	.37	.64	.26	.21
Skeptical	.30	.89	.21	.58	.13	.17

870  
871  
872  
873  
874

Factorial design with total of 516 subjects (258 per group, A or B or X or Y) comparing event rates of 37.5% vs. 27.5%

	Posterior Probability of Benefit					
	>0% reduction in death or impairment		>10% reduction in death or impairment		>20% reduction in death or impairment	
	Prior	Posterior	Prior	Posterior	Prior	Posterior
Perspective						
Neutral	.50	.99	.37	.92	.26	.66
Skeptical	.30	.98	.21	.89	.13	.60

875  
876  
877  
878  
879

Factorial design with total of 516 subjects (258 per group, A or B or X or Y) comparing event rates of 35% vs. 30%

	Posterior Probability of Benefit					
	>0% reduction in death or impairment		>10% reduction in death or impairment		>20% reduction in death or impairment	
Perspective	Prior	Posterior	Prior	Posterior	Prior	Posterior
Neutral	.50	.87	.37	.60	.26	.24
Skeptical	.30	.83	.21	.53	.13	.18

880  
881  
882  
883  
884  
885  
886  
887  
888  
889  
890  
891  
892  
893  
894  
895  
896  
897  
898  
899  
900  
901  
902  
903  
904  
905  
906  
907  
908  
909  
910  
911  
912

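### If a cell is closed, the collapsed margins are confounded by the other cooling factor; section 5.1 names only lost power, and the section 5.2 frequentist analyses do not adjust for that factor

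*Protocol*

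**What the plan says.** Figure 2 of the protocol labels the depths A (33.5°C) and B (32.0°C) and the durations X (72 hours) and Y (120 hours), giving cells AX, AY, BX and BY.

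- **Section 5.1, planning rates.** The cell rates are "AX=45%, AY=BX=30%, BY=25" percent. They give a marginal "comparison of event rates of 37.5% vs. 27.5" percent and "a sample size of 363 per group (A or B", and likewise for X or Y.
- **Section 5.1, closing a group.** Randomization to one group may stop because of adverse events, and later infants then go to the other three. The same reasoning is extended to two groups. For the margins the stated consequence is that the power of analyses as "conventionally performed for a factorial trial would be decreased". The text adds that nobody would still want the harmful treatment, and that the power to "compare these specific 3 groups would not be compromised and in actuality would be" somewhat higher than planned.
- **Section 5.2, analysis.** The main analyses are X vs Y and A vs B at the margins. Cell-wise comparisons are a secondary objective, for testing interaction. Group differences are tested by chi-square or Fisher's exact test, and robust Poisson regression gives risk ratios "adjusting for the stratification variables (level of HIE and site"). The other cooling factor is not named. The only bias of the margins that is discussed is the one due to interaction.
- **Supplement 2.** The Bayesian log-binomial model does contain depth, duration and their interaction.

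**The concern.** A collapsed margin is a clean comparison only while the other factor is equally distributed on both sides. With four equal cells, half of X and half of Y are cooled to 32.0°C. If BY closes, X remains half 32.0°C infants while Y becomes mostly 33.5°C infants, so X vs Y carries part of the depth effect. By symmetry A vs B carries part of the duration effect. Adjusting for HIE level and site cannot remove this, and it arises without any interaction.

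The contingency is one that the protocol itself raises, and section 5.1 names BY as the group possibly at highest risk of complications. If section 5.2 were followed literally after such a closure, a factor with no effect could appear harmful or beneficial. The choice of a different primary analysis would then have to be made during the trial.

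**Working it through.** **1. The plan's own figure.** Inputs from section 5.1: 37.5% vs 27.5%, two-sided 5%, 80% power, 5% loss. The two-proportion formula without continuity correction gives 343.2, so 344 per margin, and 344/0.95 = 362.1, so 363. This matches the protocol; the sample size is not in question. Evaluable infants: 726 × 0.95 ≈ 690.

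**2. Cell sizes after BY closes.** Let f be the fraction enrolled before closure, with equal allocation before it and 1:1:1 afterwards (the 1:1:1 is my assumption). Closure times are taken from the looks in section 5.3: 40 infants (f = 40/726 = 0.055), and 25%, 50% and 75% of accrual.

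- BY: 690f/4
- each open cell: 690f/4 + 690(1−f)/3

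At f = 0.25, BY = 43.1 and each open cell = 43.1 + 172.5 = 215.6.

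**3. Spurious difference.** Suppose duration has no effect and the event rate is h at 33.5°C and l at 32.0°C. The share of 32.0°C infants is 1/2 in X and w = BY/(AY + BY) in Y. Then P(Y) − P(X) = (1/2 − w)(h − l).

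At f = 0.25, w = 43.1/258.8 = 0.167. With h = 45% and l = 30% the difference is 0.333 × 15 = 5.0 points: X 37.5% (n = 431) vs Y 42.5% (n = 259), an apparent harm of longer cooling.

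**4. False-positive rate, pooled two-proportion test.** At f = 0.25 the pooled standard error is 0.0384 and the unpooled one 0.0386. Rejection in the upper direction is Φ((0.050 − 1.96 × 0.0384)/0.0386) = Φ(−0.65) ≈ 0.26; the lower tail is negligible. In the same way:

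| BY closed at | w | 45% vs 30% | 37.5% vs 27.5% | 35% vs 30% |
|---|---|---|---|---|
| 40 infants | 0.04 | 42% | 23% | 9.5% |
| 25% of accrual | 0.17 | 26% | 15% | 7% |
| 50% | 0.30 | 13% | 9% | 6% |
| 75% | 0.41 | 7% | 6% | 5% |
| never | 0.50 | 5% | 5% | 5% |

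All three pairs of rates appear in the protocol: the first in the cell rates, the second as the planned margins, the third as the smaller-effect scenario of the Bayesian tables in section 5.2. The table applies equally to A vs B with a duration effect only. If BX closes instead, the bias in A vs B reverses: with a duration effect of 45% vs 30% and closure after 40 infants, the risk ratio is 0.82 and the rejection rate 44%.

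**5. Does adjustment cure it?** Robust Poisson regression was simulated (1,500 runs per scenario) for the depth effect, with no true depth effect and duration rates of 45% and 30%:

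| BY closed at | Without duration: RR, rejection | With duration: RR, rejection |
|---|---|---|
| 40 infants | 1.18, 43% | 1.00, 6% |
| 25% | 1.13, 26% | 1.00, 6% |
| 50% | 1.08, 12% | 1.00, 5% |

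**6. Is it only power?** Take the protocol's four cell rates with BY closed after 40 infants. The crude contrast is 37.5% vs 29.8%, which is 7.7 points, with 52% power. With the same unequal margins but the planned 10 points kept, power would be about 76%. Most of the fall from 80% therefore comes from the changed composition of the margins rather than from their unequal sizes.

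**The case against.** **Section 5.1 does not stop at lost power.** It goes straight on to the three remaining groups, a comparison that avoids this confounding. A reader might infer that the protocol commits itself to biased margins after a closure; it does not say so, and section 5.2 can be read as describing the design with all four groups open. That stands. But section 5.1 never makes the three-group comparison primary, and section 5.2 confines cell-wise analyses to interaction testing, so the two sections leave the primary analysis after closure unsettled.

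**One model does contain both factors.** The Bayesian model in Supplement 2 includes them, so it would be wrong to say that no model in the document adjusts. However, the protocol synopsis makes the Bayesian analysis conditional on a smaller effect than hypothesized. The point is therefore limited to the chi-square, Fisher and robust Poisson analyses of section 5.2.

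**The largest figures need a large effect and early closure.** A reader might infer from the 42% that type I error is generally uncontrolled. The table does not support that: with 35% vs 30% it never exceeds 9.5%, and with late closure it is close to nominal.

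**Covariate lists often belong in a SAP.** True, and the SAP is not shown. The point rests on what the protocol states: its named covariates, its restriction of cell-wise comparisons, and its account of what closure does to the margins.

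**Conclusion.** The point holds in this limited form. If a cell closes, the collapsed margins are biased whenever the other factor has an effect. Section 5.1 describes only a loss of power, and the covariates named in section 5.2 do not remove the bias. With BY closed, the false-positive rate ranges from about 5% (small effect, late closure) to 42% (15-point effect, closure after 40 infants).

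This rests on 690 evaluable infants, 1:1:1 allocation after closure and no true effect of the tested factor. The direction depends on which cell closes. There is no such bias if all four cells stay open or if the other factor has no effect.

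A reader might also set the marginal contrast (61% power with BY closed at 25% of accrual) against AX vs AY (90%) and attribute the whole gap to closure. That is not supported: the two target different effects, 8.3 and 15 points, and AX vs AY already has 82% power with all cells open.

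**What to change.** - **Section 5.2.** Include both depth and duration, with HIE level and site, in the primary robust Poisson model. Base the primary inference on that model rather than on the unadjusted chi-square test.
- **Sections 5.1 and 5.2 together.** State that if a cell closes, the collapsed margins are no longer primary. Replace them either by the two-factor model with an enrolment-period term, or by pairwise contrasts among the cells still open, restricted to concurrently randomized infants. AX vs AY and AX vs BX are the right pair only if BY is the closed cell; other closures need their own contrasts. Say how the shared-control multiplicity, which section 5.2 itself raises, will be handled.
- **Section 5.1.** Amend the sentence on reduced power to say that the unadjusted margins would also be biased.

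The cost is one covariate and a few sentences. The sample size is unchanged, and with all four cells open the effect on the results should be negligible.
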